4.2 Secondary judgement criteria

- The complications of pre-hospital ECMO are evaluated by indirect criteria. The criteria chosen are:
 - Percentage of success with the implementation of ECPR. ECPR with an output of more than 2 litres per minute is considered to be successful.
 - ECPR implementation time. The time period taken into account is the time period before incision - the initiation of ECPR
 - The percentage of severe complications due to haemorrhage defined by more than 6 transfusions of packed red blood cells in the first 24 hours
 - The percentage of infectious complications defined by the presence of a systemic inflammatory response associated with a presumed or identified infection during hospitalisation in the ICU.
- The progression of patients admitted to the ICU is evaluated by monitoring:
 - With neurological assessment by the "Cerebral Performance Category" (CPC) score done on or in D 28, 2 months, and 1 year. (In conformance with the recommendations). This score is defined by:
 - Level 1: Conscious and good cerebral performance, might have mild neurological or psychological deficit.
 - Level 2: Conscious and moderate cerebral disability.

- Level 3: Conscious and severe cerebral disability.
- Level 4: Coma or vegetative state.
- Level 5: Brain death or demise
- For deceased patients, the number of patients progressing towards brain death, and the number of organs harvested.
- To identify predictive factors of success of pre-hospital ECMO.
- The predictive factors are obtained by clinical and para-clinical data collection (implementation of cerebral monitoring by cerebral tissue saturation, and a pupillometer as well as measurement of venous blood lactates...)

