Immediate complications: haemorrhage, infection

Number of organ harvesting

The quality of survivors' neurological status according to the CPC neurological classification at D 28, 2 months and 1 year

Predictive indicators of the prognosis during cardiac arrest via cerebral and biological monitoring

Inclusion criteria:

Eligible patients have the following combination of criteria:

- Adults over 18 years of age and under 65 years of age
- **And** Refractory cardiac arrest (defined by the failure of professionals to resuscitate at the 20th minute of cardiac arrest with a minimum of 3 AED or equivalent analyse)
- **And** Beginning of external cardiac massage within the first 5 minutes after cardiac arrest (no flow < 5 min.) **with** persistent shockable rhythm **or** persistent of signs of life during resuscitation (any rhythm): spontaneous movement, absence of mydriasis and/or pupillary response, spontaneous breathing movements
- **And** Medical cause of the cardiac arrest
- **And** ETCO₂ above 10 mm Hg at the time of inclusion
- **And** Absence of major co-morbidity.
- **And** ECPR team available and on-site before the 40th minute

Non-inclusion criteria:

- Children under 18 years of age
- Adults over 65 years of age
- Period of more than 5 minutes without cardiac massage after collapsing
- Known co-morbidity that compromises the prognosis for short or medium-term survival
- Cardiac arrest during transportation times

Methodology, type of study: This is a prospective randomised study of current care

Sample size (SS, power, risk): A total number of 105 patients in each group will make it possible to demonstrate at the alpha risk of 5% and a power of 1- β =90%, a significant difference in favour of early pre-hospital ECPR compared to the current practice with in-hospital ECPR.

Study procedure:

Baseline visit: patient inclusion

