When a victim of cardiac arrest with strict "no flow" for less than 5 minutes is taken under care in an out-of hospital setting, a mobile ECPR team is rushed to the spot at the 10th minute of cardiac arrest. The 2 physicians in this team verify the inclusion criteria. The patient is included when all the eligibility criteria are present, between the 20th minute and the 40th minutes of cardiac arrest. Treatment starts immediately after randomisation. The success rate and ECMO implementation time are noted and compared. The family is informed at inclusion or at intensive care arrival. The patient is informed as soon as possible, if he/she is alive.

Follow-up visit on discharge from intensive care, at day 28, at 2, 6 and 12 months.: These visits should evaluate the patient outcome. The CPC score and the number of transfusions and infections during hospitalisation are evaluated.

Duration of the study: 4 years

Participation period for one patient: 1 Year

Number of investigator sites: 4

Expected results: An increase of 5% to 20% of survival for victims of out-of-hospital refractory cardiac arrest, with a good neurological prognosis.

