7 NUMBER OF SUBJECTS INCLUDED

The hypothesis is that pre-hospital ECPR will result in success for 20% of the patients, considering that the percentage of survival with in-hospital use of ECMO is less than 5%. A total number of 105 patients per group will make it possible to demonstrate at the alpha risk of 5% and a power of $1-\beta=90\%$, a significant difference in favour of early pre-hospital ECPR compared to the current practice with in-hospital ECPR.

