9.3 Research procedure for each patient

Baseline visit: Patient recruitment and inclusion phase

When a victim of cardiac arrest with "no flow" for less than 5 minutes is taken under care in an out-of-hospital setting, a mobile ECMO team is rushed to the spot at the 10th minute. This team verifies the inclusion criteria. The patient is included and randomised when all the eligibility criteria are met as of the 20th minute of cardiac arrest. Randomisation is done by drawing of lots from an envelope. In the pre-hospital ECMO group, treatment starts immediately. In the in-hospital ECMO group, medicalised resuscitation is continued and the patient is transferred to the hospital for the implementation of circulatory support. The ECPR success rate and implementation time are noted and compared. The family is informed at inclusion or at intensive care arrival. The patient is informed as soon as possible, if he/she is alive.

Follow-up visit on discharge from intensive care , at day 28, at 2, 6 and 12 months::

These visits should enable the evaluation of the patient outcome: survival, brain death or demise. A neurological exam evaluates the CPC score. The numbers of packed red blood cell transfusions in the first 24 hours and cases of sepsis over the course of hospitalisation are noted.

At 12 months, the physician will contact the patient to evaluate the patient outcome.

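### Severe haemorrhage is defined only by a transfusion count, so a fatal bleed after six or fewer transfusions is not an event and the comparison of arms can be distorted if early mortality differs

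*Combined protocol and SAP*

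**What the plan says.** Section 3.2 makes the evaluation of complications of pre-hospital ECPR the first secondary objective. The summary in section 1 names two kinds, without ranking them: "Immediate complications: haemorrhage, infection". Section 4.2 then states that "The complications of pre-hospital ECMO are evaluated by indirect criteria" and lists four: implementation success, implementation time, haemorrhage and infection. The haemorrhage item reads "The percentage of severe complications due to haemorrhage defined by more than 6 transfusions of packed red blood cells in the first 24 hours". There is no second route to an event.

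On data collection, section 9.3 says "The numbers of packed red blood cell transfusions in the first 24 hours and cases of sepsis over the course of hospitalisation are noted". On outcome it says "These visits should enable the evaluation of the patient outcome: survival, brain death or demise". Section 4.2 adds, for patients who die, progression to brain death and organs harvested. Neither section mentions cause of death or a bleeding-related death.

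The protocol does not say when the 24 hours begin, who forms the denominator, or how a patient who dies inside the window is scored. Section 8.1.2 covers only the analysis of predictive factors, so it does not settle these questions. The summary also gives a different window for transfusions: "The CPC score and the number of transfusions and infections during hospitalisation are evaluated".

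**The concern.** To meet the criterion a patient must live long enough to receive a seventh transfusion. One who bleeds to death after six or fewer fails the definition, although the bleed was fatal. All patients are in refractory arrest, so death competes with the event being counted.

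The opportunity to be transfused before death may also differ by arm. Section 2.1.4 places pre-hospital cannulation outside any healthcare setting, while section 9.3 has control patients resuscitated and moved to hospital before cannulation. The trial's own hypothesis is that survival differs between the arms. A bleeding measure that depends on survival could therefore show a difference in bleeding where none exists, or hide a real one. That would weaken the answer to the first secondary objective.

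**Working it through.** **Is there a figure to reproduce?** Not for haemorrhage: the protocol gives no expected rate. Its one computable figure is the sample size in section 7. For 5% against 20%, two-sided alpha 5% and power 90%, the pooled-variance formula is

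n = [1.960 × √(2 × 0.125 × 0.875) + 1.282 × √(0.05 × 0.95 + 0.20 × 0.80)]² / 0.15² ≈ 100.1, so 101 per group.

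Allowing for the 5% loss in section 9.6 gives 101 / 0.95 = 106.3, so 107. The stated 105 gives 91.3% power. The figure is reasonable and has no bearing on this point.

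**Applying the rule as written**

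- Patient A bleeds, receives seven or more transfusions within 24 hours, then dies: meets the criterion.
- Patient B bleeds and dies after six or fewer: does not meet it. Section 9.3 records a death and a transfusion count, and nothing marks bleeding as the cause.
- Patient C dies early of another cause, with few or no transfusions: does not meet it, and in the data described looks the same as patient B.

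**What this could do to the rate.** Every input here is an assumption. Let h be the true proportion with severe haemorrhage and e the share of those patients who die before a seventh transfusion. If all patients stay in the denominator, recorded rate = h × (1 − e).

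| h | e = 10% | e = 25% | e = 50% |
|---|---|---|---|
| 10% | 9% | 7.5% | 5% |
| 20% | 18% | 15% | 10% |
| 30% | 27% | 22.5% | 15% |

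With 105 patients and h = 20%, the true count is 21.0. At e = 25% the recorded count is 105 × 0.15 ≈ 15.8.

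**Between arms.** With h = 20% in both arms and e = 10% in one and 30% in the other, the recorded rates are 0.20 × 0.90 = 18% and 0.20 × 0.70 = 14%. The 4-point difference is false. Exchanging the two values of e reverses its sign.

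**Dependence on survival.** Suppose 20% of patients alive at 24 hours meet the criterion and none of the early deaths do. With 30% early deaths the recorded rate is 0.20 × 0.70 = 14%; with 50% it is 0.20 × 0.50 = 10%. The arm that keeps more patients alive appears to bleed more.

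**If early deaths are excluded instead.** Take h = 20% and e = 25%, so 5% of patients die early of bleeding, and let a further 45% die early without severe bleeding. Of 100 patients, 50 remain and 15 of them meet the criterion: 15/50 = 30%, above the true 20%.

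**With bleeding deaths counted** and all randomised patients in the denominator, the first between-arm example returns to h = 20% in both arms.

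**The case against.** The strongest reply is that a transfusion count is a sensible choice in a trial that cannot be blinded (section 6). It is hard to influence, whereas attributing a death to bleeding in a patient already in refractory arrest is a judgement by people who know the allocation. Section 4.2 openly calls its measures indirect. Some of these events also show up elsewhere: a vessel injury that keeps output from exceeding 2 litres per minute is an implementation failure, and any early death is a failure on the main criterion. This argues for keeping the count visible, and the fix does so. It does not close the gap, because neither of those items identifies bleeding as the cause.

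A reader might also infer more than the documents support:

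- *That this is the main safety endpoint.* The protocol names none; haemorrhage is one of four secondary measures.
- *That the rate is understated.* This requires early deaths to stay in the denominator as non-events. The protocol does not say so, and exclusion can push the rate upward.
- *That the bias favours pre-hospital ECPR.* Control patients who die before cannulation or transfusion also fail the criterion, so the bias could run either way.
- *That every fatal bleed is missed.* Those with more than six transfusions are counted.
- *That a bleed repaired after, say, five transfusions is misclassified.* This is a preference about where to set the threshold.

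The case report form is not among the documents. If it already records cause of death, the event could be recovered, but the definition in section 4.2 would still not count it.

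**Conclusion.** The concern holds in a limited form. Followed literally, the definition classifies a fatal bleed after six or fewer transfusions as not meeting the severe-haemorrhage criterion, and nothing else described allows it to be recovered. The measure therefore mixes bleeding with survival and can bias the comparison if early mortality differs between arms. Neither the direction nor the size can be computed from the documents. The 18% against 14% contrast and the 30% against 20% reversal show only what is possible under assumed inputs. The sample size and the main criterion are unaffected. This is a cheap improvement to a secondary measure and does not threaten the trial's primary conclusion.

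**What to change.** In section 4.2, define severe haemorrhage within 24 hours of randomisation, in all randomised patients of both arms, as either (a) more than six red-cell transfusions or (b) death attributed to haemorrhage. Report (a) and (b) separately, so that the existing count is preserved, and show all deaths within 24 hours by arm beside them. This also settles the denominator and the start of the window. Surgical or endovascular repair of bleeding may be reported descriptively but need not enter the definition.

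In section 9.3, add attribution of death to haemorrhage, and time of death if it is not already recorded. Reconcile the hospitalisation-wide transfusion count in the section 1 summary with the 24-hour window in sections 4.2 and 9.3.

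The cost is a few lines of text and one or two items on the case report form. The drawback is that component (b) rests on the judgement of unblinded investigators. Showing the transfusion component and all-cause 24-hour deaths separately lets a reader see how far the result depends on that judgement.

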5 POPULATION ELIGIBILITY CRITERIA

5.1 Inclusion criteria for ill subjects

Eligible patients have the following combination of criteria:

- Adults over 18 years of age and under 65 years of age
- And Refractory cardiac arrest (defined by the failure of professionals to resuscitate at the 20th minute of cardiac arrest with a minimum of 3 AED or equivalent analyse)
- And Beginning of external cardiac massage within the first 5 minutes after cardiac arrest (no flow < 5 min.) with persistent shockable rhythm **or** persistent signs of life during resuscitation: spontaneous movement, absence of mydriasis and/or pupillary response, spontaneous breathing movements
- And Medical cause of the cardiac arrest
- And ETCO₂ above 10 mm Hg at the time of inclusion
- And Absence of major co-morbidity.
- And ECPR team available and on-site before the 40th minute

5.2 Non-inclusion criteria

The non-inclusion criteria are:

- Children under 18 years of age
- Adults over 65 years of age
- Period of more than 5 minutes without cardiac massage after collapsing
- Co-morbidity that compromises the prognosis for short or medium-term survival
- Cardiac arrest during transportation times

6 EXPERIMENTAL DESIGN

This is a multi-centre prospective superiority randomised study. The results are compared to the percentage of success of in-hospital use of ECMO. Due to the type of technology used, it is impossible to implement a blind.

7 NUMBER OF SUBJECTS INCLUDED

The hypothesis is that pre-hospital ECPR will result in success for 20% of the patients, considering that the percentage of survival with in-hospital use of ECMO is less than 5%. A total number of 105 patients per group will make it possible to demonstrate at the alpha risk of 5% and a power of $1-\beta=90\%$, a significant difference in favour of early pre-hospital ECPR compared to the current practice with in-hospital ECPR.

8 STATISTICAL ANALYSIS

8.1.1 Analysis of the main judgement criterion

The success rate of pre-hospital ECMO will be compared with the percentage of success of in-hospital ECMO by a Chi-squared test. An intermediary analysis will be done every 20 patients.

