8.1.2 Analysis of the secondary judgement criteria

The identification of predictive factors of pre-hospital ECMO success will be done first by a univariate analysis using a chi-squared test (or a Fisher's exact test if the test application conditions are not verified) for the qualitative variables, and with a Student's test (or Wilcoxon if the test application conditions are not verified) for the quantitative variables.

Next, a multivariate analysis by logistic regression will enable the simultaneous study of factors associated with the pre-hospital success of ECPR by adjustment to the different potentially confounding variables. In the multivariate model only variables that are significant in univariate at the threshold $p=0.20$ will be used. The model variables will be selected by a backward stepwise method and tested by the likelihood ratio test. The association between the success of pre-hospital ECPR and the associated factors will be expressed in odds ratio (OR) and estimated with its confidence interval at 95%.

The tests will be bilateral and a level of significance $p<0.05$ will be considered as significant.

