9.6 Methods for monitoring excluded patients

All withdrawals from the study should be documented and the investigator should specify the reason.

For patients considered to be lost to follow-up, the case report form should be filled out up to the last visit. The investigator will try his/her utmost to contact the patient, find out the reason for withdrawal from the trial and his/her health status. Patients who withdraw will not be re-included in the study. Their treatment number will not be reused. These patients will nevertheless, be monitored in a service not included in the protocol.

Lost to follow-up: we will consider a maximum of 5% of the patients in the entire cohort to be lost to follow-up.

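### Interim analyses every 20 patients have no stated purpose, boundary or stopping rule, so the 5% alpha claimed in section 7 is not protected

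*Combined protocol and SAP*

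**What the plan says.** All references are to the combined protocol and SAP.

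- Section 8.1.1, on the main criterion, has two sentences. The first sets the test: "The success rate of pre-hospital ECMO will be compared with the percentage of success of in-hospital ECMO by a Chi-squared test". The second sets the interims: "An intermediary analysis will be done every 20 patients".
- Section 7 gives the error rates: "A total number of 105 patients per group will make it possible to demonstrate at the alpha risk of 5% and a power of" 90%. It does not mention interim analyses.
- The last sentence of section 8.1.2, on secondary criteria, gives the only test threshold in the plan: "The tests will be bilateral and a level of significance" of p<0.05. The wording is general, but the sentence is not tied to the primary test or to the interims.
- Section 6 describes a superiority trial that cannot be blinded.

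The document gives no reason for the interims (efficacy, futility or safety), no boundary or alpha-spending rule, no stopping rule, no adjustment of the final test and no data monitoring committee. Sections 7 and 8 read as complete, so redaction does not explain the gap.

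**The concern.** Repeated testing of accumulating data at an unadjusted level gives more than one chance of a false positive. The 5% in section 7 is correct for one final test, but section 8.1.1 schedules many analyses beside that test. With no rule written down, nothing prevents the primary comparison from being read at p<0.05 every 20 patients and recruitment from being stopped on a favourable reading. The trial is open label, which adds to that risk.

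Two things are at stake: the type I error of the only confirmatory comparison, and the size of any effect reported after an early stop. Trials that cross an unadjusted threshold early tend to do so on a chance high, so the estimate is biased upward.

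**Working it through.** **Inputs.** From section 7: 105 per group, two-sided alpha 5%, power 90%, and "pre-hospital ECPR will result in success for 20% of the patients, considering that the percentage of survival with in-hospital use of ECMO is less than", where the control limit given is 5%. From section 8.1.1: chi-squared test (continuity correction not stated) and a look every 20 patients. From section 9.6: "we will consider a maximum of 5% of the patients in the entire cohort to be lost to follow-up".

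**Step 1: reproduce the plan's own figure.** For two proportions, pooled variance under the null, no continuity correction:

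n = [1.96·√(2·0.125·0.875) + 1.2816·√(0.05·0.95 + 0.20·0.80)]² / 0.15² = 100.06 per group.

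Allowing for 5% loss, 100.06/0.95 = 105.3, which agrees with the stated 105. The figure is that of a single-look design; it contains no allowance for interims.

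**Step 2: count the looks.** The total is 2 × 105 = 210. Counting all patients, looks fall at 20, 40, ..., 200 and 210, which is 11. Counting per group, they fall at 20, 40, 60, 80, 100 and 105, which is 6.

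**Step 3: type I error if every look is a test at p<0.05.** With n per arm, a and b successes and s = a + b, the uncorrected statistic is X² = 2n(a−b)² / [s(2n−s)]. Yates replaces |a−b| by |a−b|−1. An exact recursion over the two binomial counts, with equal arms at each look and stopping at the first X² > 1.96² in either direction, gives:

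| Common success rate | One final look | 11 looks, uncorrected | 6 looks, uncorrected | 11 looks, Yates |
|---|---|---|---|---|
| 3% | 4.4% | 10.1% | 8.9% | 1.9% |
| 5% | 4.4% | 13.3% | 11.3% | 4.0% |
| 8% | 5.2% | 16.7% | 14.0% | 5.9% |
| 12.5% | 5.2% | 18.4% | 15.0% | 8.1% |
| 20% | 5.0% | 19.0% | 15.0% | 10.4% |

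The normal-theory value for 11 looks is 19.9%. Fisher's exact test at all 11 looks gives 4.3-11.1% for rates of 5-20%. Fisher only where an expected count is below 5 gives 6.1-16.6%. False claims in favour of pre-hospital ECPR alone are half the two-sided figure: 6.7-9.5% for 11 uncorrected looks, against a nominal 2.5%.

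**Step 4: why the choice of test matters early.** At the first look there are 10 per arm. At a pooled rate of 12.5% the expected successes are 10 × 0.125 = 1.25 per arm. A split of 4 versus 0 gives X² = 20·16/(4·16) = 5.0, p = 0.025; Fisher's test gives p = 0.087.

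**Step 5: effect on the estimate.** Under 5% versus 20%, 11 uncorrected looks: 49% of trials cross within the first 60 patients (26% with Yates). The mean difference at crossing is 19.9 points (19.3 with Yates) against a true 15.

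**Step 6: the same design with a boundary.** The O'Brien-Fleming critical value at information fraction t is c/√t.

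- Looks at 70, 140 and 210, c = 2.004: z = 3.47, 2.45, 2.00, or nominal two-sided p = 0.0005, 0.014, 0.045. Overall alpha is 4.7-4.9% for common rates of 5-20%, and power is 92.6% at 105 per group.
- All 11 looks, c = 2.10: final p about 0.036, alpha 4.7-5.0%, power 91.9%.
- For comparison, a Haybittle-Peto-type rule over 11 looks (p<0.001 at interims, p<0.05 at the end) gives alpha 4.4-5.2% and power 93.4%. A Pocock-type constant limit (p about 0.010) gives 1.9-4.8% and power 84.5%.

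**The case against.** The strongest reply is that the plan never says each interim is a test at p<0.05, nor that recruitment stops on a significant result. The threshold sentence stands in the section on secondary criteria. A reader might infer that the trial's true alpha is 13-19%. The documents do not support that as a fact: the figure belongs to one reading, and it sits at the upper end of the plausible span. A 3% common rate, which fits the plan's assumption of less than 5% in the control arm, gives 10.1% uncorrected. Yates or Fisher at every look gives about 4-11% for rates of 5-20%. All of this stands, and the size must be stated conditionally.

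It does not remove the point. The interims are placed beside the primary test, the plan has one threshold, and section 8.1.1 names the chi-squared test without a small-sample fallback. The Fisher alternative in section 8.1.2 is given only for predictive factors. Most readings inflate alpha, and leaving the rule unwritten is itself the defect.

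Two further inferences fail. One is that early looks could not use the 6-month outcome. Section 4.1 allows status at ICU discharge or at 6 months, and a look can wait until 20 patients have complete outcomes. The other is that no positive interim result could be believed. A very small p-value would pass any standard boundary.

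**Conclusion.** The point holds as a gap in specification with a material consequence: the 5% alpha risk in section 7 is not protected by the analysis in section 8.1.1. The size is about 13-19% if four things are true: 20 counts all patients, every look is an uncorrected chi-squared test at p<0.05, stopping is allowed in either direction, and the common success rate is 5-20%. It is about 11-15% if 20 counts per group, and about 4-10% with Yates. On the first reading, an effect reported at crossing would average about 20 points when the truth is 15. The calculations assume equal arms at each look, and the power figures assume that all 105 per group contribute an outcome. This should be corrected before any between-arm look is taken, because it concerns the only confirmatory test and the remedy costs almost nothing.

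**What to change.** Replace the interim sentence in section 8.1.1 with one of the following.

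1. **No efficacy looks.** State that the review every 20 patients covers recruitment and safety data pooled across arms, with no between-arm comparison of the main criterion, and that the primary test is done once, at 210 patients, at two-sided 5%. The single-look design of section 7 then stands unchanged.
2. **A pre-specified boundary.** State the purpose, the number and timing of looks (counted as total patients with the primary outcome complete), the test and any small-sample correction, the boundary, the final nominal level, and who sees the results, preferably people independent of the investigators. One example is O'Brien-Fleming at 70, 140 and 210 with nominal two-sided p of about 0.0005, 0.014 and 0.045. Another is O'Brien-Fleming over all 11 looks with a final p of about 0.036. The choice among boundaries that hold alpha is the sponsor's; a Haybittle-Peto-type rule would also serve.

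Section 7 should then say which design its 5% refers to.

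The cost is a few lines of text and no extra patients: power is about 92-93% at 105 per group under either O'Brien-Fleming example, against the planned 90%. The downside is a lower chance of stopping very early. With looks at 70, 140 and 210, the same recursion under 5% versus 20% gives about 2% of trials crossing at 70 patients and 62% by 140.
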